## 15.9. Study closeout

The study closeout will be reported with justification to the participating investigators, to the ECs that have evaluated the study, and to the Scientific Committee of the study.

It is the investigator responsibility to submit the final report to EC according to local requirements.

## 17. Appendices

**Appendix C:** List of sites and participating investigators

An up to date investigator list will be kept separate and maintain regularly.

## **RECABA statistical analysis plan**

### **Data preparation**

The first task to be able to analyze the information statistically is the extraction and export of the data from the web application to the analysis tool. In our case IBM-SPSS. The application has an export routine that translates the data into Excel format. This information will later be imported into SPSS. It should be taken into account that it is not possible to attack the database directly, so the export process entails the subsequent adaptation of the variable formats for their final treatment.

Variable names are exported with the full label and starting with a digit, which is incompatible with the SPSS variable naming format. The variable names will be adapted and shortened to the SPSS format. Descriptive labels will be provided.

Categorical variables are exported using the literal of the selected option as the value. Said variables will be coded as numeric variables, with codes labeled in correspondence with the option they represent.

Date variables are exported in literal string format. These variables will be transformed into SPSS time or date variables, as appropriate, in order to perform calculations with them (for example, wait times).

The multi-response variables are stored as a combined string that collects all the choices. The multi-response variables will be translated into individual variables for each of the individual choices made.

String variables are exported with a string length (number of characters) equal to the longest tag selected. Therefore, if the longest possible label has not been selected before in an export and is selected later, the translation rules of the corresponding variable must be redefined.

No problems are expected with the export of numeric variables.

The string variables corresponding to open response fields (for example, comments or specify) will be returned to the scientific leaders of the study for coding, so that the corresponding descriptive summary can be made.

The files will be analyzed in isolation, as they are found in the application's repository, and only the relevant fields will be merged for the crossovers of variables proposed by the researchers or those proposed in this analysis plan.

### **Data export validation**

The LifeTrial tool for the collection and storage of clinical study information has a statistical summary tool (Statistics module). This tool allows defining, storing and displaying descriptive statistics of the fields contained in the electronic data collection notebook.

The data exported from the repository to SPSS (through its conversion to Excel) will be validated by comparing the statistics obtained directly with the LifeTrial Statistics tool with those obtained through SPSS. The descriptive statistics obtained with the Statistics tool basically consist of counts, bar graphs and descriptive statistics (mean standard deviation, minimum, maximum, etc.). For numerical variables (type = integer, type = decimal), the values of the summary statistics obtained with the Statistics tool will be compared with those

obtained with SPSS. Since the system does not offer summary statistics (mean, standard deviation) for date variables (type = date) (all the different recorded values are presented), subsets of data will be arbitrarily selected to check their exact export.

In any case, the number of valid data and missing data of the selected fields will be checked to ensure the correct export of the data.

### **Treatment of missing values**

The statistical analysis process assumes the correct monitoring of the data entry through the electronic data collection notebook. During the data analysis phase, no queries should be made to fill in missing information or missing values.

However, during the analysis process, missing and missing values will be identified for later treatment with the research team. Extreme and out-of-range values will also be identified for later review by the research team. The necessary corrections obtained from the identification of out-of-range values or missing information and reviewed by the patient's clinical manager will be entered into the database for subsequent treatment in subsequent re-analyses.

The initial data treatment strategy will be to assume a non-response as a completely random missing value (MCAR) and the treatment of missing values will be isolated by variable. If it is required to relate several variables in an analysis, the treatment will be "according to the pair" of variables considered (pairwise) to minimize the impact of the lost information on the estimates obtained.

In the cases in which the analysis of several consecutive measurements is carried out or the passage of time is valued, the carrying over of the last value obtained on subsequent measurements will be assumed. For example, if a subject has not suffered an event or there is no information on this aspect (missing value) at the time of closing the database, it will be assumed that the subject's status is the same as the last measurement with valid data.

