## **Follow-up**

The Follow-up table contains clinical information related to the follow-up of the patient. At the time of writing this protocol, it is unknown whether a patient can have multiple follow-up visits.

Continuous variables will be described using the statistics of central tendency (mean and median), dispersion (minimum, maximum, standard deviation and interquartile range) and shape (skewness and kurtosis). The number of valid cases and the number of cases with missing values will be reported. The continuous variables in this table are: Date of the follow-up visit, Date of post-procedure discharge, Date of admission, Date of discharge, Number of hospital stays.

The categorical variables will be described by frequencies and percentages. The number of valid cases and the number of cases with missing values will be reported. The categorical variables contained in this table are: Follow-up visit, ECG record / Monitoring type, Recurrence 3 months post-procedure, Recurrence specification, Asymptomatic AF, Treatment, Antiarrhythmics, Antiarrhythmic type, Specify, Anticoagulants, NACOs type, REDO, Type REDO, Death, Hospital stay

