### **Statistical models**

In order to conclude on the primary objective of the study, the number and percentage of cases with absence of atrial fibrillation recurrences will be calculated after 12 months of follow-up, after the cryoablation procedure. The scientific coordinators of the study will have to determine the closing date of the database so that it has been possible to collect information from 12 months of follow-up of a sufficiently large number of patients.

The protocol defines AF recurrence as a clinically diagnosed and documented episode of AF (using ECG, Holter monitor with a duration of at least 30 seconds, or using implantable devices

or event monitoring systems). The information necessary to determine the existence of a recurrence of AF will be extracted from the Follow-up and Adverse Events tables.

The existence of differences between patients with and without recurrence in clinical variables and patient follow-up will be explored. Student's t statistics (for continuous variables) and  $\chi^2$  (for categorical variables) will be used. If there are appreciable differences between the groups of patients in the clinical variables, logistic regression models will be proposed to study the multivariate effect of the variables and assess their predictive capacity.

The waiting times until the moment of recurrence of AF will be described using survival models (survival tables and Kaplan-Meier) and the existence of variables capable of predicting the differences between both groups of patients will be explored.

The necessary statistical analyzes will be approached to verify the secondary objectives based on the variables designated by the study coordinators.

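### The SAP does not exclude the 12-month AF-free percentage from its carry-forward rule and gives no denominator; if carry-forward is applied, the error can only run upward

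*SAP*

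**What the plan says.** SAP, Treatment of missing values, has two rules. The default takes non-response as missing completely at random and handles it variable by variable, pairwise when variables are related. The second covers consecutive measurements and analyses in which time matters; there, "the carrying over of the last value obtained on subsequent measurements will be assumed". The single example is a subject who "has not suffered an event or there is no information on this aspect (missing value) at the time of closing the database"; such a subject keeps the status of the last valid measurement.

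SAP, Statistical models, defines the primary result: "the number and percentage of cases with absence of atrial fibrillation recurrences will be calculated after 12 months of follow-up". It names neither missing-data rule and no denominator. The coordinators choose the closing date "so that it has been possible to collect information from 12 months of follow-up of a sufficiently large number of patients", so some subjects may lack 12-month data. Recurrence information "will be extracted from the Follow-up and Adverse Events tables". Kaplan-Meier is planned to describe time to recurrence, without a censoring rule and without a link to the primary percentage.

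SAP, Follow-up, says of that table's categorical variables, which include recurrence: "The number of valid cases and the number of cases with missing values will be reported". It also says that "it is unknown whether a patient can have multiple follow-up visits".

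In the protocol, section 9.1 sets an annual visit (plus or minus 28 days) and a 3-month blanking period. Section 9.9 foresees loss to follow-up. Section 11.2 puts AF recurrences on the adverse event form, and sections 9.6 and 11.2 require eCRF entry within 10 calendar days of awareness. Section 13 schedules the primary objective for analysis at the end of enrollment year 1, of enrollment year 2 and of follow-up. Section 13.1 mentions a previously decided allocation of lost values but does not give it.

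**The concern.** The 12-month percentage is the study's main efficacy figure, and the analyst has two written rules that give different answers. One of them, illustrated with event status at database closing, turns absence of information into absence of recurrence. A recorded recurrence is kept, so carry-forward can change an unseen recurrence into a success but never the reverse.

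A further case is not covered. A subject lost before the annual visit may have no valid follow-up value to carry. Counting that subject as AF-free also requires reading an empty adverse event record as no recurrence.

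The exposure does not depend on dropout alone. Two of the three planned analyses of the primary objective fall before all subjects can have completed 12 months.

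**Working it through.** The plan states no expected AF-free rate, loss rate or precision, so there is no planned figure to reproduce. The check shows how far the choice of rule moves the result.

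**Inputs from the documents:** about 1000 subjects, 2 years of enrollment, 1 year of follow-up each, 3-month blanking, a 28-day visit window, analyses at enrollment years 1 and 2.

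**Assumptions:** true AF-free proportion p = 75% (range 60 to 85%); no countable recurrence before month 3 and constant hazard afterwards; share m lost, with loss unrelated to outcome and uniform over the year. For the interim analyses: uniform enrollment, procedure at enrollment, no dropout.

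**Step 1. Subjects with partial follow-up.**
- Hazard: λ = −ln(p)/9 per month. At p = 0.75, 9λ = 0.288.
- Mean recurrence-free share for follow-up uniform on 0 to 12 months: M = 0.25 + 0.75(1 − p)/(9λ) = 0.25 + 0.1875/0.288 = 0.902.

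**Step 2. Carry-forward result.**
- Recurrences before loss recorded promptly as adverse events: (1 − m)p + mM.
- Recurrences recorded only at the annual visit: (1 − m)p + m.

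| Loss m | Prompt recording | Visit-only recording |
|---|---|---|
| 5% | 75.8% | 76.3% |
| 10% | 76.5% | 77.5% |
| 20% | 78.0% | 80.0% |
| 30% | 79.6% | 82.5% |

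**Step 3. Comparison with sampling error.**
- 95% half-width at n = 1000: 1.96 × √(0.75 × 0.25/1000) = 2.7 points.
- The shift exceeds this once m passes 0.0268/(0.902 − 0.75) = 18% with prompt recording (13 to 24% for p of 60 to 85%), or 0.0268/0.25 = 11% with visit-only recording (8 to 15%).
- At 5% loss the shift is 0.8 to 1.3 points, below sampling error.

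**Step 4. Loss related to outcome.** Keep 20% loss overall but let subjects with recurrence be lost twice as often.
- If the others are lost at rate a, then 0.25 × 2a + 0.75a = 0.20, so a = 0.16 and the recurrence group is lost at 0.32.
- Visit-only carry-forward gives 1 − 0.25 × 0.68 = 83.0%, a shift of 8.0 points. The m(1 − p) value of 5.0 points is therefore not a general ceiling.

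**Step 5. Planned interim analyses**, with carry-forward over all enrolled subjects.
- End of year 2: half the subjects lack 12 months. Result: 0.5 × 0.75 + 0.5 × 0.902 = 82.6% (prompt) or 0.5 × 0.75 + 0.5 = 87.5% (visit-only), against 75%.
- End of year 1: nobody has a full 12 months. Only (28/30.44)/12 = 7.7% could have had an early visit inside the window.

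**Step 6. Kaplan-Meier as the alternative** (simulation, 20% loss, no visit before loss).

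| Recording and loss | Censored at exit date | Censored at last rhythm assessment |
|---|---|---|
| Prompt, loss unrelated to outcome | 75.0% | 73.2% |
| Visit-only, loss unrelated to outcome | 77.0% | 75.0% |
| Prompt, recurrence lost twice as often | 77.2% | 75.8% |
| Visit-only, recurrence lost twice as often | 80.4% | 78.7% |

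In the last two rows every figure exceeds the true 75%.

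**The case against.** The strongest reply is that carry-forward was never meant for the percentage. The example can be read as a lay description of right-censoring, which suits the planned survival analysis. The percentage would then fall under the variable-by-variable default, that is, available cases. The valid and missing counts promised for the Follow-up table fit this reading. So does the closing-date sentence, since waiting for enough subjects with 12 months matters most when those subjects form the denominator. That sentence may also restrain a premature 12-month figure.

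This stands as a plausible reading, but no text settles it. The promised counts belong to the Follow-up field, whereas primary status is combined from two tables. The closing-date sentence gives no number, and protocol section 13 still schedules the two earlier analyses. Returning missing values to the research team may reduce them but sets no rule for those that remain.

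It is also fair that this is a descriptive, single-arm registry with no success threshold, and that no loss rate is documented. The 10-day eCRF rule favours prompt recording, so visit-only recording is an extreme, although AF found only at the visit remains possible. Both points limit the severity; neither supplies the missing rule.

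**Conclusion.** The point holds as a conditional one and should be fixed. The omission is certain: the carry-forward rule is not excluded from the primary percentage, and no denominator is given. The direction is also certain if the rule is applied. The size is illustrative: 3.0 to 5.0 points at 20% loss with p = 75% and loss unrelated to outcome, negligible at 5% loss, and larger if subjects with recurrence are lost more often.

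Three stronger readings are tempting, and the documents do not support them.
- A reader might infer that the SAP prescribes carry-forward for the primary result. It does not; available cases remains possible.
- A reader might infer that every subject without 12-month information would count as AF-free. Those with an earlier recorded recurrence would not.
- A reader might take 82.6 to 87.5% as a forecast of the year-2 report. It is what results only if carry-forward is applied to all enrolled subjects and the percentage is reported at that point.

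**What to change.** - In SAP, Treatment of missing values and Statistical models, state that carry-forward does not apply to AF recurrence.
- Estimate 12-month freedom from AF recurrence by the planned Kaplan-Meier method with a 95% confidence interval. Censor subjects without recurrence at their last follow-up or exit date, never at database closing. Add censoring at the last rhythm assessment as a sensitivity analysis.
- Report as supportive the crude percentage among subjects with 12-month information or an earlier recurrence, with its denominator and number missing, and say whether a visit inside the 28-day window before month 12 counts. This percentage can run low, because early recurrences stay in while recurrence-free subjects who are lost drop out. With prompt recording and 20% loss it is 0.60/(0.80 + 0.20 × 0.098) = 73.2%.
- At the interim analyses, report how many subjects have reached 12 months. Give no 12-month estimate at the end of enrollment year 1.

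The cost is SAP wording and modest extra analysis, with no added visits or tests. Visit, event and exit dates are already listed; the date of the last rhythm assessment must be derived from the visit date and the monitoring field. At p = 75% and n = 1000 the Kaplan-Meier half-width is 2.9 points at 20% loss, against 2.7 with complete data. At year 2 it is 3.3 points, against 3.8 for the 500 completers alone. The figure may be less favourable. Kaplan-Meier still assumes that loss is unrelated to outcome, and if that fails the two censoring dates do not bracket the truth.

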## 13.1. Analysis of clinical data

It is expected to include approximately 1000 subjects enrolled at approximately 30 Spanish sites, with an enrollment period of 2 years and a follow-up period of one year from the time of enrollment of each subject. The subjects analyzed will be the ones included in the RECABA study database: "Spanish Registry of Cryoballoon Ablation". The variables analyzed will be those mentioned previously with the intention of adequately describing the activity of the clinical sites, the procedures used and the diseases treated in accordance with standard clinical practice.

All the data are anonymized in origin so that it is not possible to identify the subjects.

The collection of data will be prospective from the time of enrollment.

The database will be received codified and debugged, and the allocation of the lost values that have been decided previously.

The basic report at the end of enrollment and at the end of the follow-up period will consist of: The quantitative variables are expressed as mean, median, typical deviation and interquartile range depending on which is most suitable for the distribution of values. The differences between groups in relation to the quantitative variables will be evaluated through the student t test for independent samples or the analysis of variance (depending on the number of groups compared) and between variables through the student t test for related samples or the analysis of variance of repeated measures, as applicable. To analyze the relationships between categorical variables the chi-squared test ( $\chi^2$ ) and the Fisher's exact test will be used. The differences of proportions will be assessed through the homogeneity test  $\chi^2$ . To assess the relationships between the quantitative variables the Pearson or Spearman r correlation will be used, as appropriate.

The intermediate statistical reports proposed by the investigators will depend on the hypotheses suggested by the investigator. They will include at least a descriptive analysis such as the one described previously. In addition, the appropriate models to respond to the hypotheses proposed will be estimated, which can include techniques of the style of exploratory factor analysis, analysis of multiple contingency, analysis of logistical regression, analysis of conglomerates or analysis of multifactorial variance.

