### **Descriptive analysis of the data**

The data repository is structured in 6 tables: Inclusion, Baseline data, Procedure, Follow-up, Adverse event and Study exit. Summary information will be provided on the variables collected in each of the tables.

Regarding dates, the time elapsed between dates or waiting times will be calculated as specified by the scientific coordinators of the study.

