### **Study exit**

The Study Exit table contains clinical information regarding the patient's study exit.

This table only contains two variables: the reason for leaving and the date of departure. Both variables will be adequately described by frequency of the reasons and the calculation, for their description and summary, of the corresponding waiting times.

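### The SAP applies last-value carry-forward to time-based analyses and gives no censoring date, so its Kaplan-Meier analysis can count unobserved time as AF-free

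*SAP*

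**What the plan says.** **The carry-forward rule.** The SAP section Treatment of missing values sets its scope as "In the cases in which the analysis of several consecutive measurements is carried out or the passage of time is valued". In those cases "the carrying over of the last value obtained on subsequent measurements will be assumed". The example that follows concerns a subject who has had no event, or about whom nothing is known, "at the time of closing the database, it will be assumed that the subject's status is the same as the last measurement with valid data".

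**The analysis it meets.** SAP, Statistical models: "The waiting times until the moment of recurrence of AF will be described using survival models (survival tables and Kaplan-Meier"). Time to recurrence is plainly an analysis in which time matters, so it falls within the rule.

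**What is left open.** Neither document names a censoring date. On waiting times, the SAP (Descriptive analysis of the data) says only that "the time elapsed between dates or waiting times will be calculated as specified by the scientific coordinators of the study". Statistical models leaves the database closing date to the same coordinators.

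**How long subjects are observed.** Protocol 13.1 plans about 1000 subjects "with an enrollment period of 2 years and a follow-up period of one year from the time of enrollment of each subject". Protocol 9.1 schedules one annual visit, within 28 days either side, and a 3-month blanking period. Protocol 6.1 puts the whole study at about 3 years and allows follow-up to be extended. For subjects who leave, the SAP describes the Study exit table thus: "This table only contains two variables: the reason for leaving and the date of departure".

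**The concern.** Kaplan-Meier already deals with incomplete follow-up. A subject without the event contributes time up to the last observation and then leaves the risk set. Carrying a no-event status forward defeats this, because it keeps people in the risk set while nobody is looking for the event.

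Two consequences would follow:

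- **After month 12.** Early enrollees would appear event-free for many months beyond their annual visit. The curve would run nearly flat with hundreds apparently at risk. The synopsis gives long-term results as part of the registry's purpose, so readers could take that stretch as evidence of durable freedom from AF.
- **At month 12.** Subjects lost before the annual visit would remain in the risk set as AF-free, which pushes the 12-month Kaplan-Meier value up.

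**Working it through.** **1. Reproduce the planned duration.** Enrollment of 24 months (Protocol 8.1, May 2016 to May 2018) plus 12 months of follow-up for the last subject gives 24 + 12 = 36 months. This matches the 3 years in Protocol 6.1.

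**2. Unobserved time under the literal reading.** Unobserved time = closing date minus last observation. Assume the procedure takes place at enrollment.

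| Database closes at month | Most added, 12-month completer | Most added, subject lost just after the procedure |
|---|---|---|
| 12 (end of enrollment year 1) | 0 | 12 |
| 24 (end of enrollment year 2) | 12 | 24 |
| 36 (end of follow-up) | 24 | 36 |

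The rows are the three analysis times in Protocol 13. With closing at month 36, a completer enrolled in month *m* gains 36 − 12 − *m*, so the range is 0 to 24 and the mean is 12 if accrual is even. The visit window shifts the maximum by 28/30.44 = 0.92 months, to between 23.1 and 24.9.

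**3. Shape after month 12.** Assumptions not in the documents: even accrual, closing at month 36, no recurrence counted before month 3, a constant hazard in months 3 to 12, 25% recurrence by month 12, no loss, and no recurrence recorded after month 12.

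- Hazard: λ = −ln(0.75)/9 = 0.03196 per month.
- Mean observed time: 3 + 0.25/λ = 3 + 7.82 = 10.82 months.
- Mean time counted to closing: 10.82 + 0.75 × 12 = 19.82 months.
- Apparently at risk at month 24: only those enrolled in the first 12 of 24 months can reach it, so 1000 × 0.5 × 0.75 = 375, on a curve still reading 75%.

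The documents give no late recurrence rate, so I put no figure on how far that 75% would be from the truth.

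**4. Value at month 12.** Let *p* be true recurrence by month 12 and *q* the proportion lost, spread evenly over months 0 to 12 and unrelated to recurrence. Everyone has at least 12 months between procedure and closing, so the literal curve at month 12 is 1 minus the proportion with a recorded recurrence:

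S(12) = 1 − [(1 − q)p + q·r], where r = (9 − p/λ)/12 is the chance that a lost subject recurs before being lost, and λ = −ln(1 − p)/9.

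For p = 0.25, r = (9 − 7.82)/12 = 0.098. At q = 0.10: 1 − (0.225 + 0.0098) = 0.765. At q = 0.20: 1 − (0.200 + 0.0196) = 0.780.

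| True AF-free at month 12 | r | 0% lost | 5% lost | 10% lost | 20% lost |
|---|---|---|---|---|---|
| 80% | 0.078 | 80.0 | 80.6 | 81.2 | 82.4 |
| 75% | 0.098 | 75.0 | 75.8 | 76.5 | 78.0 |
| 70% | 0.119 | 70.0 | 70.9 | 71.8 | 73.6 |

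**5. Same data, censored at last observation.** Simulating 200,000 subjects with true values of 80% and 70% returns the true 12-month value to within 0.001 at every loss rate in the table. The upward shift therefore comes from the carry-forward and not from the losses themselves.

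**The case against.** The strongest reply is that the rule carries a status and never says that time at risk runs to closing. In the SAP sentence, the phrase about closing the database can be attached to the condition, as the moment when information is found to be missing. It need not be the date to which the status is extended. Recording no event as of the last valid measurement is ordinary censoring, and the coordinators could specify waiting times that way.

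This stands in part. A reader might infer that the SAP prescribes Kaplan-Meier time to closing; it does not say so. But ordinary censoring needs no carry-forward, so the benign reading leaves the rule with nothing to do in survival data. The rule also expressly reaches subjects with no information, and no competing censoring date exists. The choice changes the curve, so it should not be left open.

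Other points that stand:

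- Time after month 12 is not wholly unobserved on paper. Protocol 11.2 collects AF recurrence as an adverse event throughout the study, Statistical models draws recurrences from that table, follow-up may be extended, and the SAP does not know whether subjects will have several follow-up visits. Still, no visit or monitoring after the annual visit is fixed, and absence of a report does not show absence of AF.
- With no early loss, the 12-month value is right even under the literal reading.
- One could compute a large fall in recurrences per person-year. No such rate is planned, so it is not a measure of harm here.

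**Conclusion.** The concern holds in limited form. The SAP states a carry-forward rule for time-based analyses, ties its example to database closing, and gives no censoring date for the time-to-recurrence analysis. Followed literally, it puts unobserved AF-free time into the curve.

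The size depends on assumptions. The 0 to 24 added months apply to completers with closing at month 36 and exactly 12 months of follow-up. A reader might take 24 as a ceiling for every subject, but an early loss can gain up to about 36. Extending follow-up would shrink the part after month 12 and leave the early-loss part in place. At 10% to 20% early loss, the 12-month Kaplan-Meier value rises by about 1.2 to 3.6 percentage points across true values of 80% to 70%. The documents give neither the loss nor the recurrence rate.

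A reader might also infer that the primary result is wrong because of the plateau. The documents do not support that: the primary result is the number and percentage recurrence-free at 12 months, and the curve beyond month 12 does not enter it. This should be corrected before the curve is produced.

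**What to change.** In the SAP, Treatment of missing values, exclude time-to-event analyses from the carry-forward rule. In Statistical models, add:

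- Subjects without a documented recurrence are censored at their last documented rhythm assessment (follow-up visit or recording).
- Subjects with no post-procedure assessment are censored at the last date they were documented as seen, for example post-procedure discharge. Neither the administrative exit date nor database closing is used. Protocol 9.9 declares loss only after three failed contact attempts, so the exit date can fall well after the last observation and would put unobserved time back in.
- Curves show numbers at risk and are not interpreted beyond scheduled follow-up (month 12 plus 28 days, or the extended period). Later recurrences reported as adverse events are listed separately.

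The cost is a few sentences. The SAP already lists the follow-up visit date, the post-procedure discharge date and the procedure date. It lists no separate date for a rhythm recording, so the visit date would serve where none is captured. The price is a slightly less favorable 12-month curve when there are early losses, and a shorter curve.
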